# **STUDY SUMMARY**

Full study title	SkIN hydrAtion evaluation with TeRAhertz scanning
Short study title	SINATRA Study
Study aim	Pilot study to confirm feasibility, test recruitment, trial procedures and refine intervention delivery.
Study design	Single centre, non-randomised, Pilot trial
Study participants	Patients with suspected/confirmed skin cancer and patients with benign dry skin conditions
Study arms	
 
Benign dry skin condition group
 
Skin cancer group (either confirmed basal cell carcinoma and/or suspected malignant melanoma)
 

Sample size	150 (ratio of 2:1 so 100 in the skin cancer group and 50 in the benign dry skin condition group) Within the skin cancer group we will aim for 50 basal cell carcinoma patients and 50 malignant melanoma patients
Planned study period	24 months
Planned recruitment start date	15/03/2022
Planned recruitment end date	15/03/2023
Planned study end date	30/03/2024
Objectives	
 
To undertake a feasibility study
 
To assess skin hydration and confirmed/suspected skin cancer water content with terahertz imaging.
 

Primary Objective	The primary objective will be to explore the feasibility, test recruitment, trial procedures and refine intervention delivery
Secondary Objective	To explore if Terahertz skinometry can quantify skin hydration and will show an increase in skin water content after application of an emollient in dry skin conditions.  To explore if Terahertz skinometry can quantify skin hydration and many indicate the presence of residual basel.
	hydration and may indicate the presence of residual basal cell carcinoma after primary excision, or the localised inflammation caused by melanoma skin cancer.

Key Words: SKIN; CANCER; TERAHERTZ; IMAGING; DIAGNOSIS; NOVEL

Figure 1: Participant Flow Chart

<sup>1There will typically be 7 quality THz scans in this arm of the study. Areas of interest may be scanned up to a maximum of 3 times at each time point in order to ensure a clear image is received.

<sup>2There will typically be 3 quality THz scans in this arm of the study. Once identified, each area will be scanned up to a maximum of 3 times to ensure a meaningful datasets acquired. If multiple cancerous areas are identified, the one that gives the clearest image will be chosen. This may involve scanning multiple cancerous areas before a decision is made as to which area is most suitable to pursue.

Table 1: Schedule of Events – Skin Cancer Group

Procedure	Screening	Study visit 1* – before surgery	Surgery	Post-surgery
Eligibility	X 			
Assessment				
Invitation to take	Х			
part				
Informed consent		X		
Baseline data		X		
collection				
Medical History		Х		
Current		X		
Medications				
THz scan of		X		
control area				
THz scan of		X		
cancer area				
THz scan of		X		
reference				
standard (volar				
forearm)				
Skin surgery			Χ	
Histology results	·			X
Adverse events		Х	Х	Х

Table 2: Schedule of Events – Benign Dry Skin Condition Group

Procedure	Screening	Visit 1* – before emollient application	Emollient application to dry skin area and control area	Visit 1* - 10 minutes after emollient application	Visit 1* – 20 minutes after emollient application
Eligibility	$X^1$				
Assessment					
Invitation to	X				
take part					
Informed		X			
Consent					
Baseline data		X			
collection					
Medical		Х			
History					
Current		Х			
Medications					
THz scans of		Х			

reference standard area				
(volar				
forearm)				
THz scans of	X		Χ	X
control area				
THz scans of	X		X	X
dry skin area				
Emollient		Χ		
application of				
dry skin and				
control area				
Adverse	 X	Χ	X	X
events				

<sup>1 It will be our endeavour to screen prospective participants before there scheduled visits at the dermatological clinic however, considering this is an observational study prospective participants can be screened/recruited on the day they visit (baseline) the dermatological clinics for their scheduled appointments.

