Study arm 2: The arm with 100 patients with known or suspected skin cancer will have a scan with the THz skinometer in the clinic prior to their planned skin surgery. They will be scanned on the cancerous area, a control area and a reference standard area (the volar forearm) for a minimum of 3 quality scans. In the event that the reference standard and control area are the same, then the participant will only have a minimum of 2 quality scans. The purpose of the reference standard area scan is to act as a calibration point and so we can compare a between subject variable as well as the within subject variable from the cancer/control area. If a participant has multiple potentially cancerous areas on their body, the team will decide which of these areas to scan for the study. If it occurs that the chosen area is too difficult to scan/doesn't produce a clear enough image then a different cancerous area will be selected. There will be a maximum of 3 scans conducted at each of the cancerous area, control area and reference standard area in order to obtain a meaningful dataset. Later the results of the THz scan will be compared to the formal histology results after the primary (melanoma) or residual (BCC) tumour has been removed.

For patients with multiple skin conditions (i.e. multiple dry skin or cancerous locations on the body), we will select the area that is most practical to scan and can make good contact with the scanner.

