## 7.3 Trial assessments

After patient recruitment, individuals will have a photo taken of the area of skin to be scanned before being scanned with the THz skinometer. A non-toxic Easi-Mark Surgical Skin Marker will be used to draw around the area to be scanned for image registration (both study arms) and to control the amount of skin product applied in the fixed area (study arm 1 only). This will be performed by a delegated research team member in an appropriate environment as per standard trust policy.

- A. **Study arm 1**: A minimum of 6 (most likely 7) readings of the THz skinometer ("scan") will be conducted after measuring the area of interest (AOI) and area of unaffected skin (control area measurement), at the following time points:
  - 1. Pre-application THz skinometer ("scans") of the AOI and area of unaffected skin, and the reference standard (volar forearm)

- 2. Post-application scan-I: participant will then be requested to apply emollient used regularly by them to the dry skin and control area, following which after 10 minutes another THz skinometer ("scans") will be conducted of the AOI and control area
- 3: Post-application scan-II: Repeat scans of AOI and control area will be conducted 10 minutes following the post-application scan-I

Further scans may be required if a clear image is not received upon the first attempt. At each time point each area will be scanned a maximum of 3 times to ensure a clear image is received.

Following the completion of the scans this will be the end of participation in the trial and the patient will continue the standard treatment pathway.

**Study arm 2**: A minimum of 2 (most likely 3) readings of the THz skinometer ("scan") will be conducted after measuring the AOI, area of unaffected skin (control area measurement) and the reference standard (volar forearm).

As with study arm 1; each area can be scanned up to 3 times to ensure a clear image is received. If a participant has multiple cancerous areas on their body the team will select the area most appropriate/feasible to scan. If they are unable to receive a good image, they will select another area instead.

This will be the end of participation in the trial and the patient will continue the standard treatment pathway. Histological diagnosis will be collected remotely using patient notes/medical records at a later date (typically 2-4 weeks after biopsy) by a delegated research team member.

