For all consenting eligible patients, during the study visit, outcomes will be taken for the affected (area of interest) and unaffected (control) parts of the skin. For each group, a paired t-test will be used to compare the means of outcomes (e.g. skin hydration) for affected and unaffected parts. The corresponding mean difference between affected and unaffected parts and 95% confidence interval (CI) will also be reported. For affected parts, using one way analysis of variance (ANOVA), we will test whether the means for the three groups are equal. Pairwise comparisons using independent t-tests will also be performed, with mean difference and 95% CI reported. We will also compare unaffected parts means for the three groups similarly.

Since this is a feasibility study, we will test all hypotheses at 10% significance level. Also, we will not adjust for multiplicity associated with testing multiple hypotheses. However, for it to be worthwhile conducting a future large study to test utility of THz, clear signals (large differences), estimated using mean differences and 95% CIs, will need to be observed in this feasibility study.

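### For skin cancer participants with several lesions, one section picks the analysed lesion by comparing THz images and two others do not; the rules need reconciling, and the comparative one could bias the lesion-control difference

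*Protocol*

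**What the plan says.** The protocol gives the lesion-selection rule for the skin cancer arm in several places.

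- **Study Summary, Figure 1, footnote 2:** "If multiple cancerous areas are identified, the one that gives the clearest image will be chosen". It adds: "This may involve scanning multiple cancerous areas before a decision is made as to which area is most suitable to pursue".
- **Section 1.4, study arm 2:** "the team will decide which of these areas to scan for the study". A different lesion is taken if the chosen one proves too hard to scan or its image is not clear enough.
- **Section 1.4, closing paragraph (both arms):** "we will select the area that is most practical to scan and can make good contact with the scanner".
- **Section 7.3:** "the team will select the area most appropriate/feasible to scan", followed by "If they are unable to receive a good image, they will select another area instead".

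Repeat scanning is symmetrical. Section 1.4 states for this arm: "There will be a maximum of 3 scans conducted at each of the cancerous area, control area and reference standard area".

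The selected lesion is the affected skin in section 8: "For each group, a paired t-test will be used to compare the means of outcomes (e.g. skin hydration) for affected and unaffected parts". It also enters the one-way ANOVA and the pairwise comparisons across the three groups. Section 8 tests at 10% without multiplicity adjustment, and makes a future large study depend on large differences, judged from mean differences and 95% confidence intervals.

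**The concern.** Footnote 2 is a comparative rule applied after the images have been seen. Sections 1.4 and 7.3 choose first and substitute on failure. An operator with two lesions that both scan adequately keeps the clearer one under footnote 2 and the first one chosen under the other sections. Testing trial procedures is part of the primary objective (section 3.1), so a core scanning procedure should not have two answers.

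The comparative rule also uses the modality under study to decide which lesion is analysed. Section 1.6 reports good THz contrast between BCC and normal tissue and relates it to higher water content. If operators read contrast as clarity, they would tend to keep lesions with more of the hydration signal that section 8 tests. For the control area, repeat scans are allowed but no comparison of candidate sites by image is described. The mean difference and interval that inform the decision on a larger study could then be shifted upward.

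The Study Summary also lets one participant have both BCC and suspected melanoma. For such a person, the lesion chosen would also settle the analysis group.

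**Working it through.** **1. The rules side by side, for two lesions that both scan adequately**

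| Place | Basis of choice | When the lesion changes | Lesion analysed |
|---|---|---|---|
| Summary, footnote 2 | Clearest image | After comparing images | The clearer one |
| 1.4, arm 2 | Team decision | Difficult to scan or not clear enough | The one first chosen |
| 1.4, closing paragraph | Practicality and contact | Not stated | The most practical one |
| 7.3 | Appropriateness or feasibility | No good image obtained | The one first chosen |

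The conflict is in the text and needs no assumption.

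**2. The plan's own figure.** Section 8.1 gives 80% power for the independent t-test with 50 per group, a standardised difference of 0.5 and a 10% level. The noncentrality is 0.5 × √(50/2) = 2.5, and Φ(2.5 − 1.645) = 80.4% (79.9% with the noncentral t). The figure reproduces as two-sided and does not depend on how lesions are chosen.

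**3. Size of a possible shift.** The protocol gives none of these inputs, so all are assumptions:

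- f, the share of participants with two candidate lesions: 0.2 to 0.3;
- r, the correlation between image clarity and the lesion reading: 0.3 to 0.5, with 1 as the limit;
- lesion and control readings independent with equal SD, the two lesions independent, and selection among sites on the lesion side only.

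The expected maximum of two standard normals is 1/√π = 0.564. The mean lesion reading therefore rises by 0.564 × f × r in SDs of that reading. The paired difference has an SD √2 times larger, so the shift in SDs of the paired difference is 0.564 × f × r / √2.

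| f | r | Shift (SD of paired difference) | Rejection at nominal 10%, n = 50, no true difference |
|---|---|---|---|
| any | 0 | 0 | about 10% |
| 0.2 | 0.3 | 0.034/1.414 = 0.02 | about 10% |
| 0.3 | 0.5 | 0.085/1.414 = 0.06 | about 13% |
| 0.3 | 1 | 0.169/1.414 = 0.12 | about 22% |

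A simulation on the same assumptions agrees. With f = 0.25, two lesions and r = 0.5 it gave 0.049 SD, against 0.25 × 0.5 × 0.564/1.414 = 0.050 from the formula. With three candidate lesions it gave 0.078 SD (rejection 15%). At r = 0 there was no shift in any setting.

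**4. Scale.** The half-width of the 95% interval for a paired difference with n = 50 is about 1.96/√50 = 0.28 SD. A shift of 0.06 is about a fifth of that (0.06/0.28 = 0.21), and 0.12 is about two fifths (0.12/0.28 = 0.43).

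**The case against.** The strongest reply is that footnote 2 selects on clarity, while section 8 tests outcomes such as hydration, and the protocol never equates the two. Where it explains an unclear image (section 1.4, dry skin arm), the reason is access and positioning, and the closing paragraph of section 1.4 speaks of contact with the scanner. If that is all clarity means, the comparison is unbiased. This stands: the link to water content is plausible for BCC from section 1.6 but is not established, and no figure is given for it.

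A reader might infer that affected skin in general is a best-of-several reading set against an unselected control. The documents do not support that. Only skin cancer participants with several lesions are touched, and only where footnote 2 is followed. Control and reference areas may also be scanned up to three times; the asymmetry is confined to choice among sites.

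A reader might also infer that the decision on a larger study is compromised. Section 8 asks for large differences, not rejection at 10%, and shifts of 0.02 to 0.12 SD are small beside the 0.5 that section 8.1 calls moderate (there for independent groups). The primary feasibility endpoints in section 3.3 do not depend on lesion choice.

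Selection that changes someone's group needs one person with both lesion types. The protocol allows this but gives no frequency.

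Finally, a numeric quality limit and sensitivity analyses may properly sit in an SAP. The conflict between sections is different: it concerns a scanning procedure that the protocol itself sets out.

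**Conclusion.** The contradiction stands: footnote 2 compares images and keeps the clearest, while sections 1.4 and 7.3 choose first and replace only on inadequate imaging. The bias is possible but not shown. It needs participants with several lesions, use of footnote 2, and clarity that tracks water content. Under the assumed inputs the upward shift is about 0.02 to 0.06 SD of the paired difference, with 0.12 SD at the limiting correlation, and zero if clarity reflects only contact or positioning. Correlation between lesions in the same person would lower these values; more candidate lesions or a larger multi-lesion share would raise them. Sample size and stated power are unaffected. The point is worth acting on because the rules must be reconciled anyway, and removing the comparative one costs almost nothing.

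**What to change.** Put one rule in the Study Summary footnote, section 1.4 and section 7.3:

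- Before any THz scan, name the index lesion, and with it the BCC or melanoma group, on non-THz grounds such as accessibility and likely scanner contact. Choose among lesions listed for the planned surgery, so that the scan can be matched to histology.
- Replace it only if it fails an image-adequacy criterion applied alike to lesion, control and reference areas, and never because another lesion images more clearly.
- Log every area scanned and rejected, with the reason. This is also useful feasibility data.
- Repeat the paired analysis without substituted lesions as a sensitivity analysis.

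Fixing the lesion by list order alone would ignore the need for scanner contact and is not needed. The cost is protocol wording, one more field on the scan form, and occasionally analysing a less clear image than was available.

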# LIST OF ABBREVIATIONS

2WW	Two-week Wait
BCC	Basal Cell Carcinoma
CCG	Clinical Commissioning Group
CI	Chief Investigator
CRF	Case Report Form
CRRS	Clinical Results Reporting System
СТ	Computed Tomography
GCP	Good Clinical Practice
GMP	Good Manufacturing Practice
IB	Investigator Brochure
ID	Identification
ICF	Informed Consent Form
ICH	The International Council for Harmonisation of Technical
	Requirements for Pharmaceuticals for Human Use
ISF	Investigator Site File
NHS	National Health Service
NHS R&D	National Health Service Research & Development
PC	Personal Computer
PI	Principal Investigator
PIS	Participant Information Sheet
PPI	Patient and Public Involvement
R&D	Research & Development
RCT	Randomized Control Trial
REC	Research Ethics Committee
SC	Stratum corneum
SINATRA	SkIN hydrAtion evaluation with TeRAhertz scanning
SOP	Standard Operating Procedure
THz	Terahertz
TMF	Trial Master File
TMG	Trial Management Group
TSC	Trial Steering Committee
UHCW	University Hospitals Coventry and Warwickshire NHS Trust
UoW	University of Warwick

## 1. INTRODUCTION

## 1.1 Background

Medical imaging commonly involves the use of radiation, such as x-rays, that can give detailed images of internal structures of the body but can carry a small risk of tissue damage due to the radiation involved. As such, the number of x-rays and computed tomography (CT) scans that an individual can have has to be minimised. Methods have recently been developed that make use of electromagnetic radiation for imaging purposes at terahertz (THz) frequencies, the region of the spectrum between millimetre wavelengths and infrared. Terahertz spectroscopic imaging uses low power levels such that adverse effects on tissues are insignificant and is safe for in vivo imaging of humans [1]. The terahertz region is between the radio frequency region and the optical region generally associated with lasers. Both the IEEE RF safety standard and the ANSI Laser safety standard have limits into the terahertz region. The focus of this project is to investigate THz spectroscopic imaging as a new and powerful tool for analysing skin properties, termed "THz skinometry". The novelty in this project lies in tailoring the instrumentation and algorithms of THz scanning to accurately measure properties of human skin (e.g. hydration levels and skin thickness) in vivo. The customised non-contact and pressure-controlled contact THz probes developed will be able to do spectroscopic measurements of skin in vivo at the molecular level. This will be the first demonstration of in vivo THz imaging of skin globally and will facilitate quantitative characterisation of skin in a way that has hitherto not been possible and could lead to a step change in THz technology usage (similar to that currently used in airport security scanners).

## 1.2 Proposed study

The SINATRA study is pilot study with a primary aim to explore the feasibility of the trial methodology. In addition, secondary objectives of the study will investigate if THz light is able to detect subtle differences in skin hydration and their clinical relevance. Due to the unprecedented sensitivity of THz light to skin hydration, we will also investigate if different skin types have a preferential uptake of certain emollients. This would include dry skin conditions such as eczema, psoriasis and post-operative scars. This will give us information on how to optimise the types of emollients used in future development of new moisturisers and sunscreens. This is already under investigation in a cohort of volunteers with unaffected skin (unpublished pilot study data, University of Warwick). Additionally, as part of the SINATRA study, we will investigate if THz imaging is able to detect subclinical (invisible) skin cancer (residual basal cell carcinoma (BCC)) and enhance the diagnosis of suspected skin cancer (malignant melanoma) in vivo. Skin cancer is known to produce a localised inflammatory reaction and microscopic swelling and so the changes in skin hydration may be able to be objectively measured by THz skinometry.

Terahertz scanner (Investigational Medical Device) and safety:

Terahertz ( $10^{12}$  Hz) pulsed imaging is a new technique with high resolution and has only emerged recently as a potential new clinical tool for medical imaging. It is a safe imaging modality as the light is non-ionising – it has a million times lower energy than an x-ray and thus doesn't have enough energy to cause ionisation. The power levels used in the THz systems in this study are also very low such that there are no lasting effects. In particular, our *in vivo* THz imaging systems have a peak power less than 40mW and average power intensity less than 4  $\mu$ W/cm². Studies by Hough et al [2] have shown that even using peak power 50,000 times higher and an average intensity 30 times higher does not cause any change in gene expression. Therefore, power levels used in our THz in vivo imaging systems are safe and have no known side effects or risks

## 1.3 Study population

The SINATRA study will collect preliminary pilot data from participants in a two-arm feasibility observational study.

- One arm will consist of 100 patients with known or suspected skin cancer (skin cancer defined as: incompletely excised BCC with histologically proven radial margin involvement; biopsy proven BCC, or pigmented lesions suspicious of malignant melanoma). Images will be taken in the clinic prior to planned skin surgery and later compared to the formal histology results after the primary (melanoma) or residual (BCC) tumour has been removed.
- 2. The second arm will consist of 50 patients with benign dry skin conditions (eczema, psoriasis, skin grafts, scars etc.) and will compare the water content of their skin before and after application of a propriety emollients in common usage (e.g. E45®, Aveeno®, Doublebase®). This will add to the existing dataset that has been recorded from healthy non-patient volunteers (unpublished data, University of Warwick). This may help to guide patient-specific emollient selection in the future.

This will add to the knowledge base to define the appearance of skin cancers under THz skinometry. The spectroscopic findings will not influence the established management that will have been planned in conjunction with a Consultant Dermatologist or Plastic Surgeon and the patient.

